8.2.6.3. Acute Systemic Allergic Reaction

Management of acute systemic allergic reactions will be at the discretion of the investigator, taking into account the following protocol procedures (see also Table 2), and should follow generally accepted medical standards.

Grade 1

A Grade 1 acute systemic allergic reaction is defined as localized urticaria (wheals) with no medical intervention indicated.

Participants may continue study intervention or have their study intervention interrupted at the investigator's discretion. The participant should be advised to contact the investigator immediately if there is any worsening of the pruritus, or if any systemic signs or symptoms develop. Antihistamines or topical corticosteroids or antipruritic agents may be prescribed as long as these are in line with the (dis)allowed medications as indicated in Section 6.7, Concomitant Therapy, or in the local Prescribing Information of the ARV agents.

Grade 2

A Grade 2 acute systemic allergic reaction is defined as localized urticaria with medical intervention indicated, or mild angioedema with no intervention indicated.

Participants may continue study intervention or have their study intervention interrupted at the investigator's discretion. If there is any worsening of the allergic reaction, the participant should be advised to contact the investigator immediately and to discontinue study intervention. Antihistamines or topical corticosteroids or antipruritic agents may be prescribed as supportive care as long as these are in line with the (dis)allowed medications as indicated in Section 6.7, Concomitant Therapy, or in the local Prescribing Information of the ARV agents.

Grade 3

A Grade 3 acute systemic allergic reaction is defined as generalized urticaria, or angioedema with intervention indicated or symptoms of mild bronchospasm. Participants will permanently discontinue study intervention. Participants will be treated as clinically appropriate. Standard management should be undertaken.

Grade 4

A Grade 4 acute systemic allergic reaction is defined as acute anaphylaxis, or life-threatening bronchospasm, or laryngeal edema. Participants will permanently discontinue study intervention. Participants will be treated as clinically appropriate. Standard management should be undertaken.

Acute anaphylaxis, or

larvngeal edema

life-threatening bronchospasm, or

Permanently discontinue study

intervention

DAIDS Toxicity	Definitions	Investigator Action
Grade 1	Localized urticaria (wheals) with no medical intervention indicated	Participant may continue study intervention
Grade 2	Localized urticaria with intervention indicated, or mild angioedema with no intervention indicated	Participant may continue study intervention
Grade 3	Generalized urticaria, or angioedema with intervention indicated, or symptoms of mild bronchospasm	Permanently discontinue study intervention

Table 2: Summary of Allergic Reaction Follow-up

8.2.6.4. Potential Renal Toxicity

Grade 4

Estimated creatinine clearance (eCrCl) will be calculated according to the Cockcroft-Gault formula will be followed post baseline during the treatment phase. The eGFRs calculations will be performed and provided to the investigator by the central laboratory. Any participants who have an eCrCl of <50 and a decrease of 20% in eCrCl from baseline, or who have other clinical and/or laboratory evidence of acute renal failure will be discussed with the sponsor's medical monitor and may permanently discontinue study intervention.

The eCrCl calculations will be performed and provided to the investigator by the central laboratory. Participants with negative or trace proteinuria at baseline who develop >1+ proteinuria on urinalysis must have urinalysis repeated, with a concurrent urine and serum chemistry, within 2 weeks of receipt of results. Upon confirmation of proteinuria, participants will be asked to return to the site for a scheduled or unscheduled follow-up visit. It is recommended that the investigator contacts the sponsor's medical monitor to discuss if further consultation with a nephrologist is clinically warranted.

Once an individual participant has developed any of these renal changes and the above management guidelines have been applied, it is not necessary to further unscheduled repeat evaluations if it is determined that it is safe for the participant to continue on treatment with standard visits as described in the protocol.

8.2.6.5. Potential Posterior Uveitis Cases

In a 9-month toxicology study conducted in dogs, some animals administered the highest dose of TAF (12 to 18 mg/kg) had minimal mononuclear cell infiltration in the posterior uvea, considered secondary to general debilitation; this finding did not occur in animals given lower doses and it has not occurred in other animal studies. This preclinical finding has also not been observed in humans where the dose is much lower, nor have there been reports of posterior uveitis in human clinical studies. Nonetheless, if participants develop signs or symptoms of posterior uveitis, which include notable eye pain or redness, reduced visual acuity, or "floaters", investigators in this study should inform the sponsor's medical monitor and determine, based on their medical judgment, the need for

ophthalmologic evaluation including dilated fundoscopy, and if required, optical coherence tomography.

8.2.6.6. Hyperglycemia

Grade 3: 13.89 to 27.75 mmol/L (250-500 mg/dL)

Grade 4: >27.75 mmol/L (>500 mg/dL)

Toxicity management decisions should be based on fasted results. If elevated glucose levels are from a nonfasted blood draw, the draw must be repeated after an 8-hour fast.

Participants who experienced asymptomatic glucose elevations of Grade 3 and participants with preexisting diabetes who experienced asymptomatic glucose elevations of Grade 4 may continue study intervention unless clinical assessment foresees an immediate health risk to the participant. Appropriate clinical management of hyperglycemia must be started in a timely fashion if applicable. Participants with persistent Grade 3 or 4 glucose elevations despite appropriate anti-hyperglycemic treatment should permanently discontinue study intervention.

For those participants with treatment emergent hyperglycemia, initiation of medications to address these AE should be prescribed in accordance to national treatment guidelines (See page 6: Figure 2 in Appendix 11: Management of Hyperglycemia in Type 2 Diabetes, 2018. A Consensus Report by the American Diabetes Association (ADA) and the European Association for the Study of Diabetes (EASD).

Should a participant have a need to initiate treatment with any excluded concomitant medication, it is recommended that investigators consult with the sponsor medical monitor beforehand to determine if an alternative therapy could be utilized that has no known impact on weight or if the participant should be discontinued from the study. If an excluded medication is initiated before discussion with the medical monitor, the investigator must notify the sponsor as soon as becoming aware.

Investigators are reminded that certain medications may influence body weight changes and should be avoided. (see disallowed concomitant therapy below). Participants should not initiate therapy with concomitant medications associated with significant weight changes during the course of the study as listed in Exclusion Criteria No. 11.

Participants who experience clinically significant changes in body weight during the course of the study may require dose reductions or withdrawal of medications to treat type II diabetes in order to avoid events such as hypoglycemia. As part of routine care at scheduled follow-up visits, participants should be assessed to determine if a dose reduction or withdrawal of medications for the treatment of such conditions is warranted. These changes should be recorded in the CRF.

8.2.6.7. Hypertriglyceridemia and Hypercholesterolemia

Hypertriglyceridemia: Grade 3: 5.7 to 11.4 mmol/L (>500-1,000 mg/dL)

Grade 4: >11.4 mmol/L (>1,000 mg/dL)

Hypercholesterolemia: Grade 3: ≥7.77 mmol/L (>300 mg/L)

Grade 4: Not applicable

Toxicity management decisions should be based on fasted results. If elevated lipid levels are from a nonfasted blood draw, the draw must be repeated after an 8-hour fast.

Participants who experienced asymptomatic triglyceride or cholesterol elevations of Grade 3 or 4 may continue study intervention unless clinical assessment foresees an immediate health risk to the participant.

Hypertriglyceridemia and hypercholesterolemia should be treated according to the specific guidelines for treating HIV-positive participants (see Figure 4 in Appendix 9: Characteristics, Prevention, and Management of Cardiovascular Diseases in People Living with HIV by American Heart Association. The presence or absence of other significant cardiovascular risk factors, which include smoking, age, family history of premature cardiovascular disease, diabetes, hypertension, low high-density lipoprotein (HDL), and prior history of cardiovascular disease should be taken into account. Appropriate clinical management of hyperlipidemia in the setting of HIV should be started in a timely fashion if applicable and taking into account the disallowed medications (refer to Section 6.8, Concomitant Therapy).

8.2.6.8. Lipodystrophy/Fat Redistribution/Body Changes

Investigators are requested to avoid using the term 'lipodystrophy acquired' or 'fat redistribution' to describe and report body fat abnormalities, as these terms are not descriptive nor fully accurate. The different symptoms and gradings are listed in the DAIDS grading table (Appendix 7: DAIDS Table for Grading the Severity of Adult and Pediatric Adverse Events) under Endocrine/Metabolic. The following terms are included: lipohypertrophy, lipoatrophy, and gynecomastia. Although metabolic abnormalities such as hyperlipidemia or hyperglycemia are often associated with body changes, these events should be recorded separately at AE reporting.

8.3. Adverse Events, Serious Adverse Events, and Other Safety Reporting

Timely, accurate, and complete reporting and analysis of safety information from clinical studies are crucial for the protection of participants, investigators, and the sponsor, and are mandated by regulatory agencies worldwide. The sponsor has established Standard Operating Procedures in conformity with regulatory requirements worldwide to ensure appropriate reporting of safety information; all clinical studies conducted by the sponsor or its affiliates will be conducted in accordance with those procedures.

Adverse events (AEs) will be reported by the participant (or, when appropriate, by a caregiver, surrogate, or the participant's legally acceptable representative) for the duration of the study.

For further details on AEs and SAEs (Definitions and Classifications; Attribution Definitions; Severity Criteria; Special Reporting Situations; Procedures) as well as product quality complaints, refer to Appendix 4: Adverse Events: Definitions and Procedures for Recording, Evaluating, Follow-up, and Reporting.

8.3.1. Time Period and Frequency for Collecting Adverse Event and Serious Adverse Event Information

All Adverse Events

All AEs and special reporting situations, whether serious or non-serious, will be reported from the time a signed and dated ICF is obtained until completion of the participant's last study-related procedure, which may include contact for follow-up of safety. Serious adverse events, including those spontaneously reported to the investigator within 30 days after the last dose of study intervention, must be reported using the SAE Form. The sponsor will evaluate any safety information that is spontaneously reported by an investigator beyond the time frame specified in the protocol.

Serious Adverse Events

All SAEs occurring during the study must be reported to the appropriate sponsor contact person by study-site personnel within 24 hours of their knowledge of the event.

Information regarding serious adverse events will be transmitted to the sponsor using the Serious Adverse Event Form and Safety Report Form of the CRF, which must be completed and reviewed by a physician from the study site, and transmitted to the sponsor within 24 hours. The initial and follow-up reports of a serious adverse event should be transmitted electronically or by facsimile (fax).

8.3.2. Follow-up of Adverse Events and Serious Adverse Events

Adverse events, including pregnancy, will be followed by the investigator as specified in Appendix 4: Adverse Events: Definitions and Procedures for Recording, Evaluating, Follow-up, and Reporting.

8.3.3. Regulatory Reporting Requirements for Serious Adverse Events

The sponsor assumes responsibility for appropriate reporting of AEs to the regulatory authorities. The sponsor will also report to the investigator (and the head of the investigational institute where required) all suspected unexpected serious adverse reactions (SUSARs). The investigator (or sponsor where required) must report SUSARs to the appropriate IEC/IRB that approved the protocol unless otherwise required and documented by the IEC/IRB.

8.3.4. Pregnancy

All initial reports of pregnancy in female participants or partners of male participants must be reported to the sponsor by the study-site personnel within 24 hours of their knowledge of the event using the appropriate pregnancy notification form. Abnormal pregnancy outcomes (eg, spontaneous abortion, fetal death, stillbirth, congenital anomalies, ectopic pregnancy) are considered SAEs and must be reported using the SAE Form. Any participant who becomes pregnant during the study must be promptly withdrawn from the study.

Because the effect of the D/C/F/TAF FDC on sperm is unknown, pregnancies in partners of male participants included in the study will be reported as noted above.

Follow-up information regarding the outcome of the pregnancy and any postnatal sequelae in the infant will be required.

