D/C/F/TAF FDC tablets should be dispensed under the supervision of the investigator or a qualified member of the study-site personnel, or by a hospital/clinic pharmacist. D/C/F/TAF FDC tablets will be supplied only to participants participating in the study. Returned D/C/F/TAF FDC tablets must not be dispensed again, even to the same participant, unless the bottles are unopened. Whenever a participant brings his or her D/C/F/TAF FDC tablets to the study site for pill count, this is not seen as a return of supplies. D/C/F/TAF FDC tablets may not be relabeled for use by other participants. The investigator agrees neither to dispense the D/C/F/TAF FDC tablets from, nor store it at, any site other than the study sites agreed upon with the sponsor. Further guidance and information for the final disposition of unused D/C/F/TAF FDC are provided in the Site Investigational Product Procedures Manual.

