6.6. Continued Access to Study Intervention After the End of the Study

Participants will be instructed that D/C/F/TAF FDC will not be made available to them after they have completed/discontinued D/C/F/TAF FDC and that they should return to their primary physician to determine standard of care.

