7. DISCONTINUATION OF STUDY INTERVENTION AND PARTICIPANT DISCONTINUATION/WITHDRAWAL

7.1. Discontinuation of Study Intervention

- A participant's study intervention must be discontinued if:
- The participant withdraws consent to receive assigned study intervention.
- The investigator believes that for safety reasons or tolerability reasons (eg, AE) it is in the best interest of the participant to discontinue study intervention.
- The participant becomes pregnant while taking study intervention (Refer to Appendix 5: Contraceptive and Barrier Guidance and Collection of Pregnancy Information). Study intervention should discontinue only after the participant has obtained alternative ARV therapy through a health care provider.
- The study is discontinued at the request of the sponsor, concerned regulatory agency, or Independent Ethics Committee/Institutional Review Board (IEC/IRB).
- The participant experiences unacceptable toxicity (as defined in Section 8.2.6, Toxicity Management).

A participant's study intervention may be discontinued if:

• An SAE occurs.

- The participant fails to comply with the protocol or study staff requirements.
- Intercurrent illness that would, in the judgment of the investigator, affect assessments of clinical status to a significant degree.
- The participant starts disallowed treatment, or requires new onset treatment with one of the disallowed medications (please refer to Section 6.8, Concomitant Therapy).
- The participant experiences virologic rebound; if genotypic/phenotypic resistance to study intervention is determined, study intervention may be discontinued, and the participant will be referred for continued medical care outside of the study.
- The investigator considers, for any other reason, it is in the best interest of the participant that he/she is withdrawn. The sponsor should be contacted for further discussion and final decision.

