7.2. Participant Discontinuation/Withdrawal From the Study

A participant will be withdrawn from the study for any of the following reasons:

- Lost to follow-up
- Withdrawal of consent
- Death

When a participant withdraws before completing the study, the reason for withdrawal is to be documented in the CRF and in the source document. If the reason for withdrawal from the study is withdrawal on consent, then no additional assessments are allowed.

Withdrawal of Consent

A participant declining to return for scheduled visits does not necessarily constitute withdrawal of consent. Alternate follow-up mechanisms that the participant agreed to when signing the consent form apply (eg, consult with family members, contacting the participant's other physicians, medical records, data base searches) as local regulations permit.

Withdrawal of consent should be an infrequent occurrence in clinical studies³², therefore, prior to the start of the study the sponsor and the investigator should discuss and reach a clear understanding of what constitutes withdrawal of consent in the context of the available reduced follow-up mechanisms listed.

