8. STUDY ASSESSMENTS AND PROCEDURES

Overview

The Schedule of Activities (SoA) summarizes the frequency and timing of metabolic, efficacy, safety, PROs, and other measurements applicable to this study. Additional visits may be required if, in the investigator's opinion, further clinical or laboratory evaluation is needed.

When an HIV-1 RNA repeat testing is required at an unscheduled visit to confirm protocol virologic rebound, an HIV-1 genotype/phenotype plasma sample and a plasma storage sample should also be drawn at the same unscheduled visit. Findings during these unscheduled visits or assessments need to be reported in the eCRF.

Some flexibility in the planning of the visits is allowed, however, the total treatment duration at the end of the study period should be 48 weeks. All study visits through Week 48 are to be completed within ± 7 days of the protocol-specified visit date.

All PRO assessments (BSQ-8D, HIV-SI and PGIC [including PGIC-S]) should be completed during the study visit before any tests, procedures, or other consultations to prevent influencing participant perceptions. The PGIC and PGIC-S should be completed after the participant completes the BSQ-8D and HIV-SI.

Other measurements may be done earlier than specified timepoints if needed. Actual dates and times of assessments (if applicable) will be recorded in the source documentation and CRF.

Additional serum or urine pregnancy tests may be performed, as determined necessary by the investigator or required by local regulation, to establish the absence of pregnancy at any time during the participation in the study. If a serum or urine pregnancy test is positive, the participant will be withdrawn from the study. For each participant, the maximum amount of blood drawn from each participant in this study will not exceed 261 mL.

Repeat or unscheduled samples may be taken for safety reasons or for technical issues with the samples or for confirmation of virologic rebound.

Sample Collection and Handling

The actual dates and times of sample collection must be recorded in the CRF or laboratory requisition form.

Refer to the Schedule of Activities (SoA) for the timing and frequency of all sample collections.

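### For a pregnant participant taking D/C/F/TAF, the protocol's withdrawal rule can end drug supply before the alternative therapy that Section 7.1 waits for has been obtained

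*Protocol*

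**What the plan says.** Four parts of the protocol bear directly on a participant who becomes pregnant.

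- **Section 7.1** lists pregnancy among the reasons for which study intervention must be stopped ("The participant becomes pregnant while taking study intervention"), then qualifies the timing: "Study intervention should discontinue only after the participant has obtained alternative ARV therapy through a health care provider". It sets no time limit.
- **Section 8 (Overview)**: "If a serum or urine pregnancy test is positive, the participant will be withdrawn from the study".
- **Section 8.3.4**: "Any participant who becomes pregnant during the study must be promptly withdrawn from the study".
- **Section 7.2** introduces its list with "A participant will be withdrawn from the study for any of the following reasons" and names loss to follow-up, withdrawal of consent and death. Pregnancy does not appear.

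Two parts govern supply. Section 6.2: "D/C/F/TAF FDC tablets will be supplied only to participants participating in the study". Section 6.6 says of participants that "D/C/F/TAF FDC will not be made available to them after they have completed/discontinued D/C/F/TAF FDC".

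Section 4.1 asks the investigator, when a participant moves to routine care at the end of the study or on early discontinuation, to see that antiretroviral treatment continues without a gap. SAP Section 1.3 repeats this. The SAP has no rule of its own for pregnancy.

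**The concern.** Stopping study drug and leaving the study are separate events, and the protocol ties pregnancy to both in different sections with different conditions. Section 7.1 makes the stop wait for a replacement regimen. Sections 8 and 8.3.4 make withdrawal follow from the pregnancy itself. Because Section 6.2 links supply to being in the study, the second rule can overtake the first.

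What is at stake is the continuity of antiretroviral treatment in a pregnant participant, and whether sites act alike. One site may withdraw her at once; another may keep her in the study until a new regimen is arranged. Each could point to a section of the protocol in support.

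**Working it through.** No arithmetic applies to the conflict itself. The check sets the sections side by side and follows them through the possible situations.

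| Protocol section | What it governs | Trigger | Waits for alternative ARV? | Timing |
|---|---|---|---|---|
| 7.1 | Stopping study intervention | Pregnancy on study intervention | Yes | None stated |
| 8 | Study status | Positive serum or urine test | Not mentioned | None stated |
| 8.3.4 | Study status | Pregnancy during the study | Not mentioned | Promptly, undefined |
| 6.2 | D/C/F/TAF supply | Being in the study | Not mentioned | Ends with participation |
| 6.6 | D/C/F/TAF access | Completing or discontinuing the drug | Not mentioned | After that event |
| 7.2 | Study status | Three listed reasons, not pregnancy | Not applicable | None stated |

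Sections 8 and 8.3.4 do not refer to Section 7.1.

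**Situation 1: Delayed Switch Arm before the switch.** Section 2 counts the INI + TAF/FTC regimen as study intervention, but Section 6.2 says the sponsor does not supply it. Withdrawal changes study status and does not by itself end the drug. There is no supply conflict.

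**Situation 2: on D/C/F/TAF, alternative ARV already obtained.** The condition in Section 7.1 is met, drug stops, and withdrawal can follow. Sections 6.2, 6.6, 7.1, 8 and 8.3.4 are all satisfied.

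**Situation 3: on D/C/F/TAF, alternative ARV not yet obtained.** Section 7.1 keeps her on drug. Sections 8 and 8.3.4 withdraw her. Once she is withdrawn, Section 6.2 no longer supplies her. The rules pull apart here, and only here. It covers the Immediate Switch Arm from baseline and the Delayed Switch Arm after Week 24.

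**Role of Section 6.6.** Its trigger is completing or discontinuing the drug, not leaving the study. Under Section 7.1 the drug is not discontinued until an alternative is obtained, so Sections 6.6 and 7.1 agree. The loss of supply follows from Section 6.2.

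**How many participants.** Section 4.1 caps men at approximately 70%, so women make up at least about 30% × 110 = 33 participants, or 30% × 150 = 45 at the maximum size after re-estimation. These counts include women not of childbearing potential. Section 5 excludes pregnancy at entry and requires highly effective contraception for women of childbearing potential. The documents give no pregnancy rate, so no expected number can be derived. The event is nevertheless planned for: the Schedule of Activities has a urine pregnancy test at every visit from baseline for women of childbearing potential.

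**Effect on data.** Section 7.1 requires the early-discontinuation visit for anyone who stops drug for a reason other than withdrawal of consent. Section 4.2 adds only a 30-day visit where applicable. No further scheduled weights after an early stop are planned, so the choice of rule mainly moves the date of that visit. SAP Section 5.2.2 uses weights after discontinuation where available.

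**The case against.** The strongest reply is that the rules can be put in sequence. The word *promptly* in Section 8.3.4 has no time limit and Section 8 gives no timing, so a site could arrange alternative therapy, stop the drug, complete the early-discontinuation visit and then withdraw the participant. Section 4.1 points the same way by asking that treatment not be interrupted. This is a fair reading, and it defeats a stronger claim that a reader might infer: that a site cannot possibly comply with all the sections. The documents leave the order unstated; they do not rule out every order.

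The reply does not remove the conflict. Section 4.1 is general, does not mention pregnancy and does not extend D/C/F/TAF supply. Sections 8 and 8.3.4 carry no condition. The sequence would be each site's own solution.

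Other objections narrow the point:

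- A reader might infer that withdrawal ends study drug for every participant. It does not for the Delayed Switch Arm before the switch.
- A reader might take Section 6.6 as denying drug to anyone outside the study. Its trigger is different, as shown above.
- Inclusion criterion 9 requires insurance covering the INI + TAF/FTC regimen for at least 6 months, which makes a gap less likely early on. Treatment runs for 48 weeks, though, and the protocol does not say that the prior regimen is the alternative meant in Section 7.1.
- Section 7.2 does not call its list exhaustive, so the absence of pregnancy there is a secondary inconsistency.
- A reader might expect a material loss of weight data. With follow-up after an early stop already limited to one or two visits, the documents do not support that.

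**Conclusion.** The point stands for participants taking D/C/F/TAF who become pregnant before alternative ARV is in hand. For them, a literal reading of Sections 8 and 8.3.4 together with Section 6.2 can end drug supply at a moment when Section 7.1 says treatment has not yet stopped. That is contrary to Section 7.1 and to the aim in Section 4.1.

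The number affected is likely to be small and cannot be estimated from the documents. The effect on the primary analysis is negligible. It should be corrected because the possible consequence for an individual is serious and the correction is easy, not because the trial's conclusions depend on it.

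The conclusion assumes that withdrawal from the study ends participation in the sense of Section 6.2. It takes no position on which clinical rule is right.

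**What to change.** Reconcile Sections 6.2, 7.1, 7.2, 8 and 8.3.4, with a cross-reference to the continuity statement in Section 4.1. State once, and refer to it elsewhere:

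- the order and timing, in pregnancy, of stopping study intervention, ending D/C/F/TAF supply and leaving the study;
- whether the rule differs for Delayed Switch participants before the switch, whose regimen the sponsor does not supply;
- whether pregnancy is a reason for study withdrawal, so that Section 7.2 agrees with Sections 8 and 8.3.4;
- where the early-discontinuation visit falls in that order.

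The clinical team decides the content of the rule. The cost is a clarification of protocol text, with no change to the sample size, endpoints or analysis.
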